1. Title Page

Project title: Testing the Optimized AGI-K Models for Scale Up in Wajir County, Kenya

Principal Investigator: [name] MPH

Population Council-Kenya

[name]

[name] [name]

[contact]

Project location: Wajir County, Kenya

Proposed project dates: January 2022 – December 2023

Study Coordinator: [name], Program Officer

Population Council Nairobi, Kenya

[contact]

Submitted to the IRB on

[name] Date January 5, 2022

2. Summary of Proposed Research

This research involves an evaluation of modified versions of the Adolescent Girls Initiative – Kenya intervention packages in Wajir County. The initial randomized controlled trial showed a successful impact of the intervention on increasing school enrollment and delaying marriage among originally out of school girls in Wajir County. The County government of Wajir has indicated their interest in and commitment to scaling up the intervention. Population Council Kenya (PC Kenya) has received funding from the Children's Investment Fund Foundation (CIFF) to test three versions of the original intervention to a) identify an optimized model and b) prepare the county government systems for implementation.

The evaluation will test three packages of interventions. All packages will include community level conversations addressing inequitable gender norms and barriers to girls education, weekly group meetings for girls ages 11-14 that cover a range of health, life skills and financial literacy topics and a government run school feeding program. One package will have only these three components. The second package will add in-kind individual and community level incentives conditioned on meeting school enrollment targets. The third package will add a household level cash transfer conditioned on girls' school enrollment. Throughout, the focus of the intervention design will be on a model that is feasible for implementation by the county government both visà-vis delivery channels and cost.

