school at baseline, cash transfers increased enrollment to 95% - a huge improvement. Cash transfers also encouraged good will towards and participation in the health and wealth parts of the program, especially in low-resourced, socially-conservative settings. Furthermore, the two-year follow up results showed that in Wajir, the program had long-term, sustainable effects with girls who were out of school at baseline being three times more likely to still be enrolled in school, twenty percentage points less likely to be married and half as likely to have given birth. However, the cost-effectiveness evaluation showed that the true benefit of the program will likely be realized when it is able to operate at scale, at lower costs ²⁷.

Therefore, with commitment from and in partnership with the Wajir County government, this study is aiming to identify the optimized model of AGI-K for implementation at scale, via government delivery channels, vis-à-vis impact and cost. While we hypothesize that the intervention package most similar to the original AGI-K design will have the greatest impact, we remain open to learn the limits of feasibility, as well as cost calculations, when implementing via government channels.

Research Design

These questions will be addressed through a quasi-experimental, longitudinal evaluation making use of multiple channels of data collection. These methods include qualitative formative work, baseline and endline surveys of girls and their heads of household, qualitative data collection during and after the intervention, community level assessments of the school feeding program, ongoing monitoring of program activities and cost-effectiveness analyses.

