The study will use a cluster randomized controlled trial design. A sampling frame of villages in Wajir County that meet the following inclusion criteria will be constructed: a) have a functioning community health unit, b) have more male students enrolled in upper primary school levels (Classes 6, 7 and 8) as compared to girls, c) have at least one female teacher in the primary school and d) have a functioning school feeding program. Urban and peri-urban areas will be excluded. Ten villages, stratified by sub-county and village size will be randomized assigned to each study arm (see below for intervention components in each arm) for a total of 30 villages. The randomization will take place publicly with eligible village leaders in attendance to increase acceptance of the randomization results. Do to the vast geographical nature of Wajir County, the villages are quite far from one another, therefore there is little risk of contamination between study villages.

Geographical Setting

The study will take place in Wajir County, located in the mainly rural, semi-arid region of Northern Kenya, and inhabited by a mainly pastoralist, Muslim population of Somali origin. Less than a quarter of adults in Wajir are literate, half of women 20-24 were married by age 18 and the total fertility rate is 7.8 (over double the national average of 3.6) ²⁸. Girls' education outcomes are incredibly poor relative to national levels with two-thirds of girls ages 6-17 having never been to school ²⁹.

5. Intervention

There are three intervention components being tested: a) community conversation groups, b) girls' safe spaces groups and c) monetary/material incentives conditioned on school enrollment. All schools will also have a pre-existing school feeding program in place. The main target are girls ages 11-14 years old. The intervention will start at the end of April 2022 with the start of the 2022 school year and end in March 2023 during the first term of the 2023 school year.

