Cash: All payments will be conditioned on girls being enrolled in school. Enrollment will be verified during the second month of each term and payments made by the end of that month. Household heads that had an out of school girl ages 11-14 at the start of the intervention period will receive a one-time payment of 4500/ (~US\$ 41). In addition, household heads of all girls 11-14, regardless of baseline school status, will receive 1500/ (~\$13.50) each term thereafter (total of four payments). Cash transfers will be paid via Mpesa to the household head determined at the time of registration. If the household has more than one girl between the ages of 11-14, they will all be eligible for their own cash transfer.

In-Kind: Girls who are out of school at baseline will receive an in-kind incentive if they enroll in school during the first term of the 2022 school year. All girls still enrolled in school during the first term of the 2023 school year will receive another incentive. The exact incentive (e.g. a goat or a school supply kit) will be determined during the formative assessment to take place in Q1 2022. In addition, a community level enrollment target will be set at 10 percentage points above baseline enrollment. If the community meets the enrollment target at the end of the program, an in-kind project will be given that values approximately US\$5000 (e.g. building classrooms or latrines at the school) which will be implemented and monitored by the community conversation group members.

The arms are as follows:

6. Study Goals/Objectives

The overall objective of this study is to determine which modified version of the original AGI-K intervention model is optimized for scale up based on effect, feasibility and cost of delivery via government channels.

The study involves the evaluation of three different packages of interventions to enrol and retain out of school girls aged 11-14 and change social norms related to girls' education and child marriage, in Wajir. All three packages will include girls' empowerment groups and community engagement on gender attitudes, layered on top of existing school feeding programmes, plus:

- 1) In some communities, no additional incentive
- 2) In some communities, an in-kind incentive for the whole community for school enrolment and retention, as well as an in kind incentive for individual girls

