- 3) In some communities, a financial incentive conditional cash for households with girls aged 11-14, conditional on school enrolment and retention.

Based on this intervention and study design, the project will seek to answer the following questions:

- 1. What are the effects on school enrollment and retention of three different packages of interventions?
- 2. What are the effects of the interventions on gender norms attitudes at community level and timing of marriage?
- 3. What are the costs of the three different packages of interventions relative to: a) one another, b) effects of each package, c) AGI-K original model and d) benefits
- 4. Which package is most feasible for efficient delivery via existing government and community structures?

Key outcomes of interest include: % of out-of-school girls enrolled, % of enrolled girls retained each term, % of enrolled girls transitioning to the next school year, literacy and numeracy scores, individual and community level gender norms attitudes, # of weekly meals accessed at school, perceived role of school feeding in school enrolment, retention and learning, % unmarried girls who are married during the study period, cost-per girl and incremental cost per educational outcome, and cost per marriage averted/additional year unmarried (via modelling). Key monitoring indicators to tracked are: # of community conversation meetings held, # of safe spaces group meetings held, average group attendance %, # of individual in-kind incentives delivered, # of community incentives delivered, and # of cash transfers disbursed.

7. Overview Table:

		Data Ga	thering Activities	
	Formative Assessment	HH Listing	Baseline Survey	Endline Survey
Study population	Girls aged 11-14, mothers and fathers of girls aged 11-	Adult member in the household, all	Girls aged 11 to 14 and adult member in household	Girls aged 11-14 and adult member interviewed at baseline
	14, teachers, CHAs, CHVs and additional key stakeholders	households in study villages	in all study villages	
Sample size	8 girls, 8 parents, 2 male teachers, 2 female teachers, 8 community health workers and 8 additional key stakeholders	Approximately 15,000 households	1,500 girls & 1,500 parents/guardians in Wajir (50 girls per village)	1,500 girls & 1,500 parents/guardians in Wajir
Location of activity	Household	Household	Household	Household
Timing	February 2022	March/April 2022	March/April 2022	April/May 2023
Method	In-Depth Interviews	Short form	Interview	Interview

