The instruments were/will be developed by the study investigators based on previous AGI-K surveys, study outcomes and indicators to be tested and gaps in the literature. The household listing tool was developed based on previous household listing tools used in AGI-K and other studies of adolescent girls in Kenya. The quantitative survey for girls will cover topics such as: household socio-demographic characteristics; schooling history; education attainment: social assets and networks, self-efficacy, financial literacy, savings and livelihoods, marital and childbearing aspirations, birth history, reproductive health knowledge, comprehension in local language and English; excerpts from official mathematics assessments multiple standards (grades); and cognitive testing. The endline survey will include additional questions to measure exposure to the study interventions or other programs in the community. The household background survey was developed using questions from the Kenya Demographic and Health survey on household assets and living conditions. Other questions were added from previous tools used in the Kenyan context. The purpose of this tool is to collect background information that the girls might not be privy to. The tool also includes some questions on gender norms that will be used to assess changes attributable to the community-level intervention over time. The surveys will be translated into Somali. The surveys will be pilot-tested with similarly aged participants prior to the start of data collection and revised based on feedback from interviewers before data collection begins.

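### With the conversations and girls' groups in all 30 villages, the trial can compare packages but cannot attribute gender-norm change to the community component or give any package's effect against no programme

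*Protocol*

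**What the plan says.** The Summary (Section 2) describes what every arm receives: "All packages will include community level conversations addressing inequitable gender norms and barriers to girls education, weekly group meetings for girls ages 11-14", together with school feeding. It then says of the least intensive arm: "One package will have only these three components". Section 6 repeats this: "All three packages will include girls' empowerment groups and community engagement on gender attitudes, layered on top of existing school feeding programmes". The arms differ only in the incentive: none, in-kind, or cash. Ten villages go to each arm, 30 in all, and both survey rounds take place in those villages.

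Against that design, the protocol makes these statements:

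- Section 5: "There are three intervention components being tested: a) community conversation groups", followed by the girls' groups and the incentives.
- Section 6, question 1: "What are the effects on school enrollment and retention of three different packages of interventions". Question 2 asks for the interventions' effects on community gender attitudes and marriage timing. Question 3b sets costs against the effects of each package.
- Section 11, on the household questionnaire: "questions on gender norms that will be used to assess changes attributable to the community-level intervention over time".
- Section 4, Research Design: "These questions will be addressed through a quasi-experimental, longitudinal evaluation making use of multiple channels of data collection". The next paragraph calls the same study a cluster randomised trial.

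**The concern.** A component present in every village has no comparison within the trial. Section 11 nevertheless promises to attribute change in gender norms over time to such a component, which is a before-after claim about something that never varies. Questions 1, 2 and 3b name no comparator, so they can be read as asking for each package's effect against no programme.

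The results are meant to inform scale-up by the county government. Randomised comparisons can show whether the in-kind or cash package does better than the package without incentives. They cannot show that the package without incentives changes enrolment, marriage or norms at all. If background change were presented as its effect, the county could take that as evidence for a package whose own effect was never measured.

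**Working it through.** **Inputs.** Three arms of ten villages (Sections 2 and 4); 50 girls per village and 1,500 girls in total (Section 7); common components in every arm (Sections 2 and 6); the same girls interviewed in March/April 2022 and April/May 2023 (Sections 7 and 8). The display of the arms in Section 5 was missing from the text read, but Sections 2, 4 and 6 settle who receives what.

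**The plan's own figure.** 3 × 10 = 30 villages; 30 × 50 = 1,500 girls; 10 × 50 = 500 per arm. These agree with the protocol and leave no village over for an untreated group. No power calculation is given, and none is needed, because the question is what can be estimated and not how precisely.

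**What can be estimated.** For the expected change from baseline to endline, let *t* be the background change, *b* the effect of the base package (conversations plus girls' groups), *k* the added effect of the in-kind incentive and *c* the added effect of cash.

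- Base arm: *t + b*
- In-kind arm: *t + b + k*
- Cash arm: *t + b + c*

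Three arm means carry four unknowns. The village-level design matrix has rank 3 with 4 columns, because the column for *b* is identical to the column for *t*.

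| Contrast | Expression | Estimable? |
|---|---|---|
| In-kind vs base | *k* | Yes |
| Cash vs base | *c* | Yes |
| Cash vs in-kind | *c − k* | Yes |
| Base package vs nothing | *b* | No |
| In-kind package vs nothing | *b + k* | No |
| Cash package vs nothing | *b + c* | No |

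A hypothetical fourth, untreated group would have mean *t*. The rank becomes 4 and all six contrasts can be estimated. Even then the conversations could not be separated from the girls' groups, because the two always occur together and only their sum *b* appears.

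**Size, by illustration only.** Assume *b* = 0 and *c* = 10 percentage points for enrolment, and let the background change vary. None of these values comes from the protocol.

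| Assumed *t* | Base arm, before-after (*t + b*) | Cash arm, before-after (*t + b + c*) | Cash minus base |
|---|---|---|---|
| −5 | −5 | 5 | 10 |
| 0 | 0 | 10 | 10 |
| 5 | 5 | 15 | 10 |
| 10 | 10 | 20 | 10 |

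The before-after figures move one for one with *t*; the between-arm difference does not move.

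**Why *t* cannot be taken as zero.** The girls are about a year older at endline (11–14 becomes roughly 12–15). Baseline precedes a school year delayed by COVID-19. Two of the key outcomes in Section 6, enrolment among girls out of school and marriage among unmarried girls, start at zero by definition, so within one arm they can only rise whatever the package does.

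**Other material in the protocol.** The dose-response analysis of attendance (Section 8, Activity 6) compares girls who chose to attend more or less often, so it is not randomised. The original AGI-K model is named as a comparator only for costs (question 3c). Neither supplies the missing comparison.

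**The case against.** The strongest reply is that the study is comparative. Its overall objective is to choose among modified versions of AGI-K, and the hypothesis in Section 4 ranks packages against one another. The three randomised contrasts serve that purpose without bias. This stands, and a reader who inferred that the trial cannot answer its main question would be wrong.

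A reader might also infer that the protocol will report base-arm before-after change in enrolment or marriage as an effect and carry it into the other arms. No such estimator is written. Questions 1 and 2 can be read as between-package questions, and the analysis model may be in a statistical analysis plan that is not shown.

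Nor do the documents show that the cost analysis is spoiled. Question 3 puts costs relative to one another first, the key outcomes include an incremental cost per educational outcome, and cost per marriage averted is to come from modelling whose inputs are not described.

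It is fair, too, that the conversations and girls' groups are properly under test for feasibility and government delivery (question 4 and the monitoring indicators), which needs no untreated arm. Regression to the mean might be suspected because villages must have more boys than girls in upper primary. Nothing in the protocol shows that this selects temporary lows, and the county's low schooling of girls is described as a general condition.

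One could add that the Section 11 sentence describes a questionnaire and is not an analysis statement. It is still the protocol's stated purpose for those items, and it claims attribution. No analysis plan can supply a comparison that the design lacks.

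**Conclusion.** The point holds in a limited form. Attribution of gender-norm change to the community component, and the effect of any package against no programme, are not identified. Each is fully mixed with one year of background change, and the error equals that change at any sample size. Its size is unknown, and the figures in percentage points above are illustrations. The conclusion rests on two facts in the text: every village receives both common components, and no untreated or external comparator is described.

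Questions 1, 2 and 3b are answerable as between-package effects. The randomised contrasts and the choice between packages are intact, so this is a correction to what the protocol claims and not a fault that undermines the trial. The two names for the design are a labelling inconsistency that adds no weight, since Sections 4 and 8 make clear that villages are randomised.

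**What to change.** 1. Section 11: replace the attribution wording with *differences between arms in the change in gender-norm attitudes*.
2. Section 6: state that questions 1, 2 and 3b concern the effects of adding in-kind or cash incentives to the base package, and of cash versus in-kind.
3. Report before-after change in the base arm as descriptive, with no causal attribution.
4. Report cost per outcome and cost per marriage averted as increments over the base arm. Otherwise, state the external no-programme assumption used in the modelling and show results over a range.
5. Section 5: keep components a) and b), but say that they are assessed for feasibility and delivery and not for effect.
6. Describe the design throughout as a three-arm cluster randomised trial.

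The cost is a protocol edit and narrower stated claims. If effects against no programme are wanted, wording will not provide them: an untreated or delayed-start comparison group would be needed. Isolating the conversations would also need an arm in which they vary separately from the girls' groups.
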